14.17 Appendix Q: Bayesian Adaptive Design

14.17.1 Introduction

This document outlines the adaptive design framework to be used for all trials within Novartis's Modular phase II program designed to link targeted therapy to patients with pathway activated tumors.

Although the selected tumor types may vary by trial, this document outlines the design and analysis approach based on 8 example tumor cohorts:

- Lung NSCL
- Bladder
- Breast
- Colorectal
- GIST
- HNSCC
- Ovarian
- Sarcoma

Other tumor types may be considered for trials if 1) 4 or more patients are enrolled in the cohort, and 2) a reasonable estimate of the clinical benefit rate is available.

The primary endpoint is clinical benefit rate (CBR) in each cohort, with clinical benefit being assessed at 16 weeks. All patients will receive the experimental treatment for that particular trial.

14.17.1.1 Primary Analysis

We let Y_i be the response indicator for the i^{th} subject, and let R_g be the assumed probability of response within a control population and $\pi_g = \Pr(Y_i = 1 | g_i = g)$ be the underlying probability of response for group g within the trial. We transform to the logit scale for modeling purposes. Let θ_g be the mean log odds treatment effect, i.e.:

$$\theta_g = \log\left(\frac{\pi_g}{1 - \pi_g}\right) - \log\left(\frac{R_g}{1 - R_g}\right).$$

Thus, θ_g is the group specific logistic regression coefficient for group g . The primary analysis is a set of group specific tests that $\theta_g > 0$, meaning that the experimental treatment is better than the assumed control rate for that group. Thus, we wish to test the set of hypotheses.

$$H_{0g} : \theta_g \leq 0$$

$$H_{1g} : \theta_g > 0$$

We proceed in a Bayesian fashion, assigning a prior distribution (discussed below) and computing the posterior probability of H_{1g} within each group g . If, at the final analysis,

$$\Pr(\theta_g > 0 | \text{data}) > 0.80$$

Then group g will be declared a success (thus, the final analysis produces a separate decision for each group). The trial also allows for early stopping of groups, described below.

14.17.1.2 Trial Logistics

Each trial will enroll all available subjects in all cohorts for 2 years unless a cohort cap is reached, or a cohort is stopped early, or the trial is stopped early by Novartis. Each trial will enroll no more than 30 evaluable subjects in each cohort. Interim monitoring will be conducted starting after the first 30 patients are enrolled overall (across all cohorts), and continuing each 13 weeks thereafter till study enrollment closure. After that, one CBR analysis will be done after database lock. At each interim data review, response information for the various cohorts will be evaluated to determine the current $\Pr(\theta_g > 0 | \text{data})$ within each cohort, with sufficiently high/low values used to stop the cohort for success/futility. A minimum of 10 patients will be required in a cohort before it may discontinue enrollment for futility, and a minimum of 15 patients are required before discontinuing a cohort for efficacy. If a cohort stops enrolling early, the remaining cohorts will continue until the end of 2 years or until the other cohorts reach their own early stopping criteria. The final analysis will occur after the database lock for the primary CSR.

Each trial will enroll subjects in all listed cohorts. In addition, should other cohorts be identified throughout the trial, the following mechanism will be used. If another cohort is identified, it will not be placed into the statistical analysis unless 3 subjects enroll within the cohort (thus, the trial may enroll multiple additional cohorts, but a cohort will only be added to the list if at least 3 patients enroll from that cohort). Thus, it is possible (but not viewed as

likely) that multiple additional cohorts may be added to the trial if the trial has sufficient enrollment in multiple additional cohorts. In addition to sufficient enrollment, the sponsor must have a reasonable estimate of the control clinical benefit rate.

Subjects within any cohort which does not reach the minimum enrollment will be excluded from the interim and final analyses. As the study continues, early interim data reviews may be based on fewer cohorts than later interim data reviews, as the interim data reviews will include whatever cohorts have satisfied the criteria at the time of the data review.

14.17.2 Statistical Modeling

We let Y_i be the response indicator for the i^{th} subject, and let R_g be the probability of response within a control population and $\pi_g = \Pr(Y_i = 1 \mid g_i = g)$ be the underlying probability of response for group g within the trial. We transform to the logit scale for modeling purposes. Let θ_g be the mean log odds treatment effect, i.e.:

$$\theta_g = \log\left(\frac{\pi_g}{1 - \pi_g}\right) - \log\left(\frac{R_g}{1 - R_g}\right)$$

The statistical design borrows information across groups with a hierarchical model. The hierarchical model allows dynamic borrowing of information between groups such that more borrowing occurs when the groups are consistent and less borrowing occurs when the groups differ. In this way, the model is a compromise between the two alternate extremes of either a completely pooled analysis or a separate analysis in each group. We additionally incorporate a clustering mechanism that allows borrowing within clusters but treats clusters separately. This minimizes borrowing across groups that are quite different in terms of CBR.

The purpose of such an analysis (discussed in more detail in the appendix) is to produce higher power or lower type I error in situations where we see some commonality (identical effects are not required) among the groups. The model will borrow more in situations where the groups appear similar than situations where the groups appear different.

14.17.2.1 Hierarchical Model with Clustering

Our hierarchical approach involves two stages. The goal of both stages is to allow the data to drive the amount of borrowing across groups. If the data indicate a large amount of borrowing is appropriate (due to similar results), the model will borrow more and thus increase the overall power of the trial within each group. In contrast, if the data indicate a small amount of borrowing is appropriate (due to dissimilar results) the model will adjust and each group will stand more on its own. This “dynamic” borrowing property is distinct from other approaches which use a fixed informative prior or *a priori* assume an amount of borrowing across groups. Here the approach includes two stages to identify the appropriate amount of borrowing based on the data.

The first stage of model places the groups into distinct clusters. The purpose of this stage is to minimize borrowing of information across groups that appear to be quite different. Thus, for example, should 2 of the groups appear similar while the others differ significantly, the model may place a large probability on two clusters, one containing the two similar groups with the other containing the remaining groups. The model incorporates the uncertainty of the data in

this determination, producing a probability distribution over the possible clusterings. Thus, in our example, the model may consider it highly likely that the 2 similar groups are in one cluster with the remaining groups in another, but it would also retain lower probabilities on the possibility all groups are in one cluster (e.g. we are simply seeing differences in the two groups by chance) as well as other possibilities. The complete analysis averages over this uncertainty. This clustering approach is implemented through a Dirichlet Process Mixture (DPM) model, described in the appendix.

At the second stage, we place hierarchical models over the groups within each cluster (thus, conditional on the clustering, there is no borrowing of information across clusters, only within clusters). The hierarchical model assumes that the θ_g have an across groups distribution

$$\theta_g \sim N(\mu, \tau^2)$$

The across group mean μ and variance τ^2 are unknown, and hence have a prior distribution which is combined with the data to produce estimates of μ and τ^2 .

The variance component τ controls the degree of borrowing among groups. Small values of τ result in a greater degree of borrowing while large values of τ correspond to less borrowing. The parameter τ is estimated using the data, so the observed between group variation is a key component of the model behavior.

Combined, the two stages allow groups with similar results to borrow information between them (they will have a high probability of being in the same cluster) while groups with different results will borrow far less information between them (they will have a low probability of being in the same cluster).

Details of the two stages may be found in the appendix.

14.17.3 Evaluation of Trial Success and Futility

Interim monitoring will occur after the first 30 patients are on the study for 16 weeks (112 days), then every 13 weeks thereafter till study enrollment closure. At each interim data review, the groups will be evaluated for early futility and early success by comparing posterior quantities for the response rate to pre-specified early stopping criteria.

14.17.3.1 Early Futility

If there is less than 10% probability that the response rate in a group exceeds the historical rate R_g , then the group will stop enrollment early for futility. Formally, enrollment will stop early for futility if:

$$\Pr(\pi_g > R_g) < 0.10.$$

A group is only eligible for early stopping once a minimum of 10 patients has been evaluated for response in that group.

14.17.3.2 Early Success

If there is at least 95% probability that the response rate in a group exceeds the historical rate, then the group will stop enrollment early for success. Formally, enrollment will stop early for success if:

$$\Pr(\pi_g > R_g) > 0.95.$$

A minimum of 15 subjects will need to be evaluated prior to declaring a group to be efficacious.

14.17.3.3 Final Analysis

In addition, recall the final analysis will occur when both accrual and follow-up are complete in all groups, or after the database lock for the primary CSR. If, at the completion of the trial, there is at least 80% probability that the response rate in a group exceeds the historical rate, then the group will be considered a success. Formally:

$$\Pr(\pi_g > R_g) > 0.80.$$

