10.4.3 Evaluation of trial success and futility

The clinical benefit rate will be evaluated for futility and early success by comparing posterior quantities for the rate to pre-specified early stopping criteria. The evaluations are planned to occur after the first 30 patients are dosed for at least 16 weeks or discontinued, then every 13 weeks thereafter until the enrollment closure of the study. An additional CBR evaluation will be performed after the database lock for the primary CSR.

Early Futility

If there is less than 10% probability that the response rate in a group exceeds the historical rate R_g , then the group will stop enrollment early for futility. Formally, enrollment will stop early for futility if:

$$\Pr(\pi_g > R_g) < 0.10.$$

A group is only eligible for early stopping once a minimum of 10 patients has been evaluated for response in that group.

Early Success

If there is at least 95% probability that the response rate in a group exceeds the historical rate, then the group will stop enrollment early for success. Formally, enrollment will stop early for success if:

$$\Pr(\pi_g > R_g) > 0.95.$$

A minimum of 15 subjects will need to be evaluated prior to declaring a group to be efficacious.

Final Analysis

The final analysis will occur when both accrual and follow-up are complete in all groups. If, at the completion of the trial, there is at least 90% probability that the response rate in a group exceeds the historical rate, then the group will be considered a success. Formally if:

$$\Pr(\pi_g > R_g) > 0.90.$$

In addition, a group will be considered as “promising” if:

$$0.80 < \text{Pr}(\pi_g > R_g) < 0.90.$$

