10.8 Sample size calculation

The sample size was chosen by the usual criteria of obtaining adequate power for the alternative hypothesis of interest as shown in [Table 14-18](#) of Appendix Q. This hypothesis corresponds to a generally effective treatment across groups and incorporates variation in treatment effects to reflect the realistic expectation that treatment effects may differ by group. In this setting, analytical power calculations are not possible, but the design was simulated to obtain the power of the study as shown in the appendix. The sample sizes shown (minimum of 10 for futility stopping, minimum of 15 for early success and maximum of 30 as a group cap) achieve adequate power for the alternative hypothesis. The simulations included the expected variable accrual by simulating a Poisson process with expected accrual also shown in the appendix.

11 Ethical considerations and administrative procedures

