14.17.4.2 Results

A total of 8 scenarios were simulated (two accrual scenarios and four possible ‘truths’ for the clinical benefit rate). The probability of group success for each group is provided for each scenario in the below two tables.

Table 14-18 provides the probability of group success for each of the cohort – assuming expected accrual of 10 subjects/cohort and 5 subjects/cohort separately.

Table 14-18 Probability of group success

Two-year expected accrual: 10 subjects/cohort				
Group	Null	Alternative	Two	Half
Lung LSCL	0.158	0.915	0.208	0.305
Bladder	0.131	0.918	0.232	0.322
Breast	0.147	0.909	0.233	0.312
Colorectal	0.138	0.921	0.200	0.276
GIST	0.162	0.921	0.233	0.826
HNSCC	0.139	0.906	0.217	0.834
Ovarian	0.145	0.929	0.786	0.829
Sarcoma	0.135	0.939	0.758	0.852

Two-year expected accrual: 5 subjects/cohort				
Group	Null	Alternative	Two	Half
Lung LSCL	0.132	0.803	0.204	0.258
Bladder	0.140	0.830	0.196	0.265
Breast	0.160	0.807	0.232	0.261
Colorectal	0.135	0.794	0.194	0.278
GIST	0.155	0.826	0.212	0.688
HNSCC	0.140	0.820	0.190	0.657
Ovarian	0.151	0.819	0.587	0.652
Sarcoma	0.139	0.799	0.579	0.667

Entries in bold represent groups where the treatment effect is 0 (e.g. the treatment is ineffective). Thus, entries in bold are type I errors. Entries in italics appear where the treatment is effective, and thus indicate the power of the design.

Generally, type I error is controlled below 0.20 under the null scenario (the borrowing compensates for the multiple interim data reviews) and power is an increasing function of the expected sample size (power is higher in the higher accrual situation across treatment rate scenarios). In the alternative scenario there remains decently high probability of success even in the lower accruing situations. When fewer groups are effective in truth, the scenarios “half” and “two” are harder to discern. Note in any particular trial there should be a mix of high and low enrolling groups, thus some groups may enroll closer to 10 subjects while others may only enroll five. This would produce a power value somewhere between the two tables.

Power is reduced and type I error is inflated when the truth is a mixture of effective and ineffective treatment effects across the groups. Generally power is a function of the sample size.

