6.1 Clinical Benefit Rate (CBR)

Clinical benefit is determined by investigator assessment for each tumor assessment and is defined as responses of CR or PR or SD \geq 16 weeks. In addition to tumor-specific measurements (e.g., radiological assessment of tumor response for solid tumors), progressive disease will also be considered when it was indicated either as a reason based on clinical assessment for the study treatment discontinuation or as a cause of on-treatment death. CR and PR (for solid tumors) require a confirmation that is at least a minimum of 4 weeks after the initial observation of response. Subjects who had a confirmed CR/PR or SD prior to 16 weeks, but discontinued prior to 16 weeks for reasons other than progressive disease, will have their clinical benefit defined as non-evaluable; subjects who had a confirmed CR/PR or SD prior to 16 weeks, but progressed prior to 16 weeks, will be considered as not achieving clinical benefit; subjects who had CR/PR/SD occurred prior to 16 weeks, but progressed at or after 16 weeks without evidence of CR/PR/SD at or after 16 weeks, will also be considered as not achieving clinical benefit. CBR will be analyzed by comparing achieved CBR with a historical control rate of each tumor type, and if there is at least 90% probability that the response rate in a tumor type exceeds the historical rate, then the tumor type will be considered a success; it will be considered as promising if the probability is between 80% and 90%. Details for the analyses of CBR are located in Section 10.

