7.5 Other safety evaluations

ECOG performance status will be summarized by visit for SS. The number and percentage of subjects in each score (0-5) will be displayed. In addition, the shift table of ECOG value from baseline to the worst score post baseline will be presented.

ECG values will be summarized descriptively by visit for the SS. Change from baseline for each collected parameter will also be summarized. The ECG parameters to be summarized include: QTcF, HR, PR, QT, and QRS.

Cardiac imaging evaluations will only be listed.

Baseline for the safety evaluation is defined as the last non-missing measurement on or prior to the first ceritinib dose.

8 Interim analyses

Scheduled interim analysis is planned for the primary endpoint of clinical benefit rate only as required by the Bayesian Hierarchical design. The first interim analysis performs after the first 30 patients have been dosed for at least 16 weeks or discontinued then every 13 weeks thereafter until study enrollment closure. After that, one CBR analysis will be done after database lock. Interim analyses may be performed more frequently dependent on enrollment rate to avoid over-enrollment in any of the disease groups. At each interim analysis, the groups will be evaluated for early futility and early success by comparing posterior quantities for the response rate to pre-specified early stopping criteria.

There is no plan for a formal interim analysis of safety or other secondary endpoints for this study. However, for publication or other purposes, interim data review of clean data will be performed as necessary. At these interim reviews, patient demographics/baseline characteristics, the primary and secondary endpoints as applicable, and all important safety endpoints will be summarized. No formal report will be issued for these interim data reviews.

9 Determination of sample size

The sample size was chosen by the usual criteria of obtaining adequate power for the alternative hypothesis of interest as shown in the protocol Tables 4.2 of Appendix Q (same as Table 2 as shown below in Section 10.4.2). This hypothesis corresponds to a generally effective treatment across groups and incorporates variation in treatment effects to reflect the realistic expectation that treatment effects may differ by group. In this setting, analytical power calculations are not possible, but the design was simulated to obtain the power of the

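### The plan states two final success thresholds (0.80 in protocol Appendix Q, 0.90 in protocol 10.4 and the SAP), and the power cited in protocol 10.8 belongs to the 0.80 rule

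*Protocol*

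**What the plan says.** The primary analysis gives each tumour cohort its own verdict, from the posterior probability that its clinical benefit rate exceeds an assumed control rate. The cut-off for final success is stated in two ways.

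- **0.80:** protocol 14.17.1.1 and 14.17.3.3 (Appendix Q). The latter reads "If, at the completion of the trial, there is at least 80% probability that the response rate in a group exceeds the historical rate" and gives the matching formula.
- **0.90:** protocol 10.4.2 and 10.4.3, and SAP 6.1, 10.1.1 and 10.3.3. Protocol 10.4.3 reads "there is at least 90% probability that the response rate in a group exceeds the historical rate, then the group will be considered a success". Protocol 10.4.3 and SAP 6.1 also define a middle category; in the SAP, "it will be considered as promising if the probability is between 80% and 90"%.

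On sample size, protocol 10.8 relies on Table 14-18. Its sentence begins "The sample size was chosen by the usual criteria of obtaining adequate power for the alternative hypothesis of interest as shown in" and ends by naming that table. The text with the table says "Generally, type I error is controlled below 0.20 under the null scenario". SAP section 9 makes the same sample size statement but points to its own table, "as shown in the protocol Tables 4.2 of Appendix Q (same as Table 2 as shown below in Section 10.4.2").

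**The concern.** A cohort that finishes at a posterior probability of 0.85 is a success under Appendix Q and only promising under protocol 10.4.3 and SAP 6.1. This is the decision rule of the primary endpoint. Both versions are in current text, and neither document says which governs. Protocol 10.4.2 sends the reader to Appendix Q for the model. The SAP's introduction says its Section 10 is Appendix Q, although the two differ in cohorts, control rates and threshold.

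The second issue follows from the first. If Table 14-18 was produced with the 0.80 cut-off, the power that 10.8 calls adequate is not the power of the 0.90 rule in the protocol's own statistical section.

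**Working it through.** **1. Evidence in the text.** The null column of Table 14-18 runs from 0.131 to 0.162, and its text claims control below 0.20 = 1 − 0.80. SAP Table 2 runs from 0.003 to 0.126 under the null, and its text claims control at 0.10 = 1 − 0.90. This already suggests that the tables were run under different cut-offs.

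**2. Inputs, all from Appendix Q.**
- Eight cohorts, with control rates R = 0.45, 0.47, 0.50, 0.38, 0.50, 0.45, 0.47, 0.40.
- Alternative rates 0.71, 0.73, 0.75, 0.65, 0.75, 0.71, 0.73, 0.67.
- Poisson accrual with mean 10 or 5 per cohort over two years, a cap of 30 and no dropout.
- First look when 30 patients have 16 weeks on study, then every 13 weeks. Futility below 0.10 (n ≥ 10); early success above 0.95 (n ≥ 15).

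**3. Model.** The effect is θ_g = logit(π_g) − logit(R_g). Within a cluster, θ_g ~ N(μ, τ²), μ ~ N(0, 1.82) and τ² ~ IG(3, 0.5). Clusters follow a Dirichlet process with α = 2. Pr(θ_g > 0 | data) was computed by summing over all partitions of the groups, with numerical integration in place of MCMC. There were 2,500 simulated trials per scenario, and both final cut-offs were applied to the same trials. The documents do not say whether 1.82 is an SD or a variance, so both readings were run.

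**4. Results.** Entries are mean probabilities of group success. The Half and Two rows cover the effective groups only.

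| Scenario, subjects per cohort | Table 14-18 mean | 0.80 rule (1.82 = variance) | 0.90 rule (1.82 = SD) | 0.90 rule (1.82 = variance) | Table minus 0.90 rule, points |
|---|---|---|---|---|---|
| Alternative, 10 | 0.920 | 0.923 | 0.844 | 0.827 | 7.6 to 9.3 |
| Alternative, 5 | 0.812 | 0.791 | 0.638 | 0.611 | 17.4 to 20.1 |
| Half, 10 | 0.835 | 0.835 | 0.683 | 0.672 | 15.2 to 16.3 |
| Half, 5 | 0.666 | 0.650 | 0.459 | 0.433 | 20.7 to 23.3 |
| Two, 10 | 0.772 | 0.763 | 0.577 | 0.574 | 19.5 to 19.8 |
| Two, 5 | 0.583 | 0.574 | 0.381 | 0.358 | 20.2 to 22.5 |
| Null, 10 | 0.144 | 0.147 | 0.058 | 0.056 | 8.6 to 8.8 |
| Null, 5 | 0.144 | 0.135 | 0.054 | 0.047 | 9.0 to 9.7 |

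*Reproduction at 0.80.* With 1.82 as an SD, the Alternative gives 0.931 and 0.804 and the Null 0.148 and 0.143. All 12 scenario averages (effective and ineffective groups, both accruals) are then within 2 points of Table 14-18, and the largest single-cell gap is 3.1 points. With 1.82 as a variance, 11 of 12 are within 2 points and the other is off by 2.1.

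*At 0.90*, none of the 12 averages comes within 2 points under either reading. Simulation noise cannot explain this. With 1,000 trials per stated cell, the standard error of one cell is √(0.92 × 0.08 / 1000) ≈ 0.009 near 0.92 and √(0.812 × 0.188 / 1000) ≈ 0.012 near 0.81.

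**5. Check on SAP Table 2.** The same method was run on the SAP's own seven groups with 1.82 as an SD. Alternative column, in the order of the table:

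- stated: 0.924, 0.813, 0.692, 0.698, 0.611, 0.839, 0.509
- simulated at 0.90: 0.920, 0.835, 0.700, 0.711, 0.601, 0.859, 0.502
- simulated at 0.80: 0.972, 0.915, 0.854, 0.853, 0.846, 0.939, 0.747

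SAP Table 2 therefore belongs to the 0.90 rule. Its null column also fits 0.90 better, although the breast cell does not match closely (stated 0.126; simulated 0.088 at 0.90 and 0.187 at 0.80). Reading 1.82 as a variance fits ALCL poorly (0.488 against 0.611), which favours the SD reading.

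**The case against.** The strongest reply is that 0.90 plainly governs. The SAP states it wherever it gives the rule, and the protocol's main statistical section agrees. Appendix Q describes itself as a framework for a whole programme, built on example cohorts. The interim stopping rules are identical in all places, so no enrolment decision turns on the discrepancy. Table 14-18 is correct for the rule printed beside it, protocol 10.8 quotes no power figure, and SAP Table 2 gives 0.90 operating characteristics for this trial's named histologies. Re-running Table 14-18 would describe example tumour types, and the SAP says the study was terminated early, so restated power cannot change its size.

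Much of this is fair, and it limits the scope. The power overstatement concerns protocol 10.8 and Table 14-18, not SAP Table 2. The table number that SAP section 9 cites does not exist in the current appendix and may be a leftover reference.

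It does not remove the problem. Amendment 1 revised 10.4.3, 10.8 and Appendix Q together, so 0.80 cannot simply be dismissed as old text. The SAP also presents Appendix Q as the source of its primary analysis, and the label each cohort receives in the study report still depends on the threshold.

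**Conclusion.** Wrong as written. The primary decision rule has two values in current text, and any cohort with a final posterior probability between 0.80 and 0.90 changes category with the section used. The power on which protocol 10.8 relies is that of the 0.80 rule. For the 0.90 rule it is overstated by about 8 to 9 points at 10 subjects per cohort and 17 to 20 at 5 when all cohorts benefit, and by about 15 to 23 points for the effective groups when only some benefit. Type I error under the null is overstated too, 0.144 against about 0.05 to 0.06, so the 0.90 rule is stricter on false positives.

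The figures assume uniform arrivals within each cohort, no minimum size for the eight listed cohorts, and futility stops counted as failures. Counting only cohorts with at least 3 or 4 patients moves the 0.90 Alternative at 5 per cohort to about 0.64 to 0.69, still well below 0.812. A repeat of the simulation gave 0.836 and 0.633 at 10 and 5 per cohort with 1.82 as an SD, and 0.821 and 0.606 with it as a variance. All four are within one point of the values above.

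**What to change.** - Use one final threshold throughout. Since five sections already use 0.90 and two of them define the promising band, change protocol 14.17.1.1 and 14.17.3.3 to 0.90 and add the promising category there. If the sponsor meant 0.80, the other five sections need changing instead. Either way, settle it before cohorts are labelled in the study report.
- Re-run Table 14-18 at the chosen threshold and print the threshold in its title. State whether 1.82 is an SD or a variance.
- Restate power in protocol 10.8. Under 0.90 and the stated alternative, expect about 0.83 to 0.84 at 10 per cohort and 0.61 to 0.64 at 5, labelled as figures for the eight example cohorts.
- Delete the statement in SAP section 9 that its Table 2 is the same as the protocol table, correct the table reference, and correct the SAP introduction's statement that Section 10 is Appendix Q.

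The cost is wording plus a re-run of existing simulation code. The stated power becomes less favourable. Patients are not affected.
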